The lifestyle intervention will be a modified version of the DPP intervention adapted for use in groups, as used in both Look AHEAD and HELP PD^{16,19}. The core content was integrated into a DVD video series for HELP PD to assist with standardization of intervention delivery. These DVDs contain information on the physiological, emotional, cognitive, and behavioral basics of losing weight as well as adopting and maintaining an active lifestyle. Each DVD segment also has a series of questions that are then addressed in the LHA-led group sessions. The intervention, including the DVDs, will be adapted and culturally-tailored to make it comfortable and relevant to Latino participants. The physical activity program will be progressive and will focus on walking and other large muscle activities. Physical activity bouts of ten minutes and longer will be counted toward the physical activity goal, but occupational activity will not be counted towards the physical activity goal. We will also provide pedometers to enable participants to self-monitor their physical activity and to set goals for progressively increasing their activity level. Within 3 months of study onset, the goal will be to have participants engaging in 30 minutes or more of moderate intensity activity, for a total of 180 minutes per week. Specific components of the lifestyle intervention are outlined in Table 2.

Table 2. Overview of Lifestyle Intervention

Phase	Contact Schedule	Objectives
PHASE 1 Initial Lifestyle Intervention (Months 1-6)	Weekly LHA-led group meetings, with content delivered via DVD series or by community experts Individual RD sessions in months 1, 3, and 6; Session 1 to occur prior to 1 st group meeting	Knowledge : relation of body weight and fitness to disease and health; benefits of weight loss; basics of energy balance and nutrition; appropriate methods for weight loss and increasing physical activity; exercise precautions Diet : reduction of intake by 500-1000 kcal per day; increase in fruit and vegetable consumption to 5 per day; intake of ≥ 3 whole grain servings per day Physical activity : gradual progression to 180 minutes of moderate intensity exercise per week (e.g., 30 min/day of walking, 6 days/week) Behavioral skills : self-monitoring, goal-setting, self-reinforcement, stimulus control, social support, cognitive restructuring Material : core content delivered through DVD videos and community experts

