Usual dietary intake will be assessed using a widely-used food frequency questionnaire (FFQ). The FFQ provides estimates of macronutrients, micronutrients, and servings of particular foods of interest, and has been validated against food records. Although the FFQ has shortcomings, such as potential underestimation of energy, it is the most practical instrument for large intervention studies and has become the most common method for measuring usual dietary intake. Its low cost and ease of administration are also important considerations.

In addition, diet will be monitored daily by the intervention participants through completion of their diet and physical activity logs. The precision of the FFQ is sufficient to enable us to evaluate intervention group differences in diet.

f. Physical Activity

Throughout the lifestyle intervention, physical activity will be monitored via logs that are collected by the LHAs and data entered by members of the research study team. These logs include a record of the frequency and duration of physical activity and daily steps that are self-monitored using pedometers. In addition, at assessment visits, we will use the International Physical Activity Questionnaire to evaluate between group differences in physical activity, an internationally reliable and valid instrument for assessing physical activity. The IPAQ short form is a 7-item index that asks respondents the number of days per week and the amount of time per day spent in vigorous- and moderate-intensity activities and walking, during the seven days prior to the interview. Different levels of physical activity are assigned metabolic

equivalent (MET) scores based on the Compendium of Physical Activity and, using MET-minutes, can be converted to both continuous and categorical values.

g. Self-Efficacy

There are a series of four brief measures based on social cognitive theory that address 1) barriers efficacy for physical activity and weight loss, 2) task efficacy related to specific physical capacities and weight loss, 3) satisfaction with physical function and body appearance and 4) the desire to be physically competent and to lose varying percentages of weight (converted to pounds on an individual basis). These measures will be collected at baseline and all follow-up visits for all participants and are included in Appendix B.

h. Health-Related Quality of Life

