Appendix B. La Comunidad Baseline and Follow-Up Questionnaires

Physical Activity Readiness Questionnaire (PAR-Q)

Becoming more active is very safe for most people, but just to be certain, please complete the questionnaire below. Some people should check with their doctor before they start becoming much more physically active. Start by answering the seven questions below.

1. Has your doctor ever said that you have a heart condition and that you should only do physical activity recommended by a doctor?
 YES NO
2. Do you feel pain in your chest when you do physical activity?
 YES NO
3. In the past month, have you had chest pain when you were not doing physical activity?
 YES NO
4. Do you lose your balance because of dizziness or do you ever lose consciousness?
 YES NO
5. Do you have a bone or joint problem that could be made worse by a change in your physical activity?
 YES NO
6. Is your doctor currently prescribing drugs (for example, water pills) for your blood pressure or heart condition?
 YES NO
7. Do you know of any other reason why you should not do physical activity?
 YES NO

If you answered YES to one or more questions, talk with your doctor before you start becoming much more physically active.

If you answered NO to all questions, you can be reasonably sure that you can start becoming more physically active right now. Be sure to start slowly and progress gradually- this is the safest and easiest way to go.

Referred to primary care physician for medical clearance prior to participation

CURRENT PHYSICAL ACTIVITY LEVEL

VIGOROUS PHYSICAL ACTIVITY

First we are going to ask you some questions about your participation in vigorous or "hard" activities. These are activities that take hard physical effort, make you breathe much harder than normal, and cause heavy sweating.

1. In general how many days per week do you do vigorous activities like running, heavy lifting, aerobics, or fast bicycling for at least 10 minutes in a row? Do not count any vigorous activities you did for less than 10 minutes in a row. Assume that one week is seven (7) days.

CHECK ONLY ONE ANSWER

0 Days per week	4 Days per week
1 Day per week	5 Days per week
2 Days per week	6 Days per week
3 Days per week	7 Days per week

2. On the days that you do vigorous activities, how much time do you usually spend doing them? Only count the time that you spend doing vigorous activity *for at least 10 minutes in a row*. **CHECK ONLY ONE ANSWER**

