- I do not do vigorous activity for more than 10 minutes in a row
- 10-15 minutes per day
- 15-30 minutes per day
- 30-45 minutes per day
- 45-60 minutes per day
- Over 60 minutes per day

DAILY WALKING

Next we are going to ask you about your daily walking.

3. In general, how many days per week do you walk *for at least 10 minutes in a row?*
Think about all the walking you do during the day, including walking for exercise, walking to get to places (transportation), walking at work or home, or any other walking that you do during the day. Do not count any walking that you do for less than 10 minutes in a row. **CHECK ONLY ONE ANSWER**

0 Days per week	4 Days per week
1 Day per week	5 Days per week
2 Days per week	6 Days per week
3 Days per week	7 Days per week

4. On the days that you walk, how much time do you usually spend walking? Only count the time that you spend walking *for at least 10 minutes in a row.* **CHECK ONLY ONE ANSWER**

- I do not walk for more than 10 minutes in a row
- 10-15 minutes per day
- 15-30 minutes per day
- 30-45 minutes per day
- 45-60 minutes per day
- Over 60 minutes per day

5. Of the time you spend walking *for at least 10 minutes in a row*, how much of that time is spent in brisk walking that increases your heart rate and breathing faster than normal?

CHECK ONLY ONE ANSWER

- I do not walk briskly for more than 10 minutes in a row
- 10-15 minutes per day
- 15-30 minutes per day
- 30-45 minutes per day
- 45-60 minutes per day
- Over 60 minutes per day

OTHER MODERATE PHYSICAL ACTIVITY

Last, we are going to ask you about your participation in moderate activities other than walking. These are activities that take some physical effort, and increase your heart rate and breathing above resting levels, but is not as hard as vigorous activity. Please **do not include walking** in any of your answers about moderate activity.

6. In general, how many days per week do you do moderate activities like carrying light loads, playing doubles tennis, or regular bicycling, *for at least 10 minutes in a row*. Assume that one week is seven (7) days. **CHECK ONLY ONE ANSWER**

0 Days per week	4 Days per week
1 Day per week	5 Days per week
2 Days per week	6 Days per week
3 Days per week	7 Days per week

7. On the days that you do other moderate activities, how much time do you usually spend doing them? Only count the time that you spend doing moderate activity *for at least 10 minutes in a row*. **CHECK ONLY ONE ANSWER**

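### The only activity questionnaire printed in Appendix B asks about usual activity in overlapping, top-coded time bands, unlike the seven-day IPAQ the protocol describes, and no coding rule is given

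*Combined protocol and SAP*

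**What the plan says.** Section III.H.f (Physical Activity) states that at assessment visits "we will use the International Physical Activity Questionnaire to evaluate between group differences in physical activity". It adds that "The IPAQ short form is a 7-item index" on days per week and time per day, for vigorous activity, moderate activity and walking, "during the seven days prior to the interview". The answers are weighted by MET values and, "using MET-minutes, can be converted to both continuous and categorical values". The same paragraph relies on the reliability and validity of the IPAQ.

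Table 3 schedules the IPAQ at baseline and at months 6, 12 and 24. The activity logs and pedometer counts described in III.H.f belong to the lifestyle intervention, so the IPAQ is the only activity measure planned at assessment visits in both arms.

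Appendix B prints one questionnaire on amount of activity, headed Current Physical Activity Level. Item 1 reads "In general how many days per week do you do vigorous activities like running, heavy lifting, aerobics, or fast bicycling". Items 3 (walking) and 6 (other moderate activity) open in the same general way. Days per week are recorded singly from 0 to 7. Daily time is recorded only by tick-box: none beyond 10 minutes, 10-15, 15-30, "30-45 minutes per day", 45-60, or over 60.

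Table 2 in III.F.b sets the activity target as "180 minutes of moderate intensity exercise per week (e.g., 30 min/day of walking, 6 days/week").

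**The concern.** The printed form differs from the described instrument in two respects. It asks about typical behaviour with no reference week, and it replaces an amount of time with bands that are neither mutually exclusive nor closed at the top. One of the shared endpoints, 30 minutes, is the intervention's own daily example.

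Activity is one of the two behaviours the intervention sets out to change. If this is the form used, the between-arm comparison of activity depends on which box a borderline respondent ticks, and on values that an analyst would have to choose later for each band and for the open top band. A general question at month 6 also leaves unclear whether the answer describes only the period since randomization.

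**Working it through.** **1. Side-by-side comparison**

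| Feature | III.H.f (IPAQ short form) | Appendix B form |
|---|---|---|
| Items | 7 | 7 |
| Activity types | vigorous, moderate, walking | the same three, plus a brisk-walking item |
| Reference period | seven days before the interview | none; general behaviour |
| Time per day | an amount of time | six tick-boxes |
| Score | MET-minutes, continuous and categorical | no coding rule stated |
| Label | IPAQ | not labelled IPAQ |

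**2. Which boxes fit a boundary value**

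- 10 min: the lowest option (not more than 10) and 10-15
- 15 min: 10-15 and 15-30
- 30 min: 15-30 and 30-45
- 45 min: 30-45 and 45-60
- 60 min: 45-60 only

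**3. Size for someone reporting 30 minutes on 6 days**

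The plan's own figure reproduces: 30 × 6 = 180 min/week.

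Weekly minutes = days × value assigned to the band. The documents assign no band values, so midpoints are an assumption.

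- Box 15-30: possible range 6 × 15 = 90 to 6 × 30 = 180. Midpoint 22.5 × 6 = 135, which is 45 below 180.
- Box 30-45: possible range 6 × 30 = 180 to 6 × 45 = 270. Midpoint 37.5 × 6 = 225, which is 45 above 180.

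The relative error is 45 / 180 = 25% in either direction. The true value sits at the edge of both boxes.

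**4. In MET-minutes**

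The documents give no numerical MET weights. Assuming 3 to 4 METs:

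- exact minutes: 180 × 3 = 540 to 180 × 4 = 720
- lower box: 135 × 3 = 405 to 135 × 4 = 540
- upper box: 225 × 3 = 675 to 225 × 4 = 900

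**5. Open top band**

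If over 60 is coded as 60 (again an assumption), 90 min/day is understated by 1 − 60/90 = 33% and 120 min/day by 1 − 60/120 = 50%.

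**6. What can still be computed**

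Days are exact and every band but the top is bounded. Days × band value × MET therefore gives an approximate score for every respondent once values are fixed. What is lost is the exact score, resolution near 30 minutes and in the upper tail, and the seven-day basis.

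**The case against.** The strongest reply is that this may not be the IPAQ at all. The form carries a different heading and stands between the PAR-Q and the Diabetes Risk Test, both of which are screening tools. It also has a brisk-walking item that III.H.f does not mention. Section III.H has questionnaires added to Appendix B as they become available, and the appendix is visibly incomplete: the food frequency questionnaire is scheduled in Table 3 and listed on the Encounter and Disposition form, yet is not printed. The IPAQ is scheduled and listed in the same way, so it could be a separate form. This stands, and it makes the point conditional. It does not remove it, because the printed form has the same item count and activity types and is the only candidate shown.

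A reader might infer three stronger things that the documents do not support:

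- **That MET-minutes cannot be derived at all.** Step 6 shows that an approximation can be. Section III.H.f says only that scores can be converted, and the Analytical Plan (IV) names no MET-minute analysis.
- **That the error is half the weekly goal.** The 90 minutes between the two boxes is the distance between two possible answers. The error from the true value is 45. If ticks split evenly, the mean is (135 + 225) / 2 = 180, with no average bias. Nor is a participant at the goal necessarily at 30 minutes on the walking item: that item counts walking at work, while III.F.b excludes occupational activity from the goal.
- **That general questions respond slowly to change, or that the IPAQ's validity is lost.** The documents offer no evidence for the first. On the second, they show only that the validity cited is for a differently described instrument.

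**Conclusion.** The mismatch holds as a limited, conditional defect. If the Appendix B form is the one used at assessment visits, it does not deliver the seven-day record or the exact continuous score that III.H.f describes, and its time categories are not mutually exclusive. For a respondent at 30 minutes on 6 days the ambiguity is ±45 min/week (25%) around 180. That figure rests on an assumed midpoint coding and on a value lying exactly on a boundary, so it illustrates the problem and does not estimate bias between arms. Whether any misclassification would differ by arm cannot be judged from the documents.

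It would be wrong to read this as a threat to the trial's main result. Physical activity is not among the primary, secondary or tertiary outcomes in Section II, and the HbA1c comparison at one year does not use it. The consequence is confined to the between-arm comparison of activity and its interpretation.

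**What to change.** - **Preferred:** use and print in Appendix B a form that matches III.H.f, with the seven-day reference period, and record minutes per day as a number. Section III.H.f specifies only an amount of time, so the numeric entry should be stated explicitly.
- **If the banded form is kept:** make the bands exclusive (for example 10-14, 15-29, 30-44, 45-59, 60 or more), reword the lowest option as less than 10 minutes, and add the seven-day window. Analyse the bands as ordinal, or prespecify a value for each band and for the top band with a sensitivity analysis. Exclusive bands remove the double box but not the rounding: 30 minutes would always fall in 30-44, whose midpoint gives 37 × 6 = 222 min/week, 42 above 180. Midpoint coding alone is therefore not enough. Amend the continuous MET-minute and IPAQ-validity statements in III.H.f to match.
- **If a separate IPAQ form is already in use:** print it and state the purpose of the Current Physical Activity Level form.

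The cost is a form revision, plus separate coding of any data already collected on the present form.

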Two common HRQL instruments – the Short Form 36 items (SF-36) and Health Utilities Index - 3 (HUI 3) will be used in La Comunidad. The SF-36 is the most widely used general health status measure with extensive validation and population norms available. It allows comparison of the planned study population with those of other studies and other chronic diseases. Eight scale scores will be generated in the following domains: general health, physical function, role-physical, role-emotional, vitality, social function, mental health, and pain. It can also be scored in terms of physical health and mental health component scores. The Health Utilities Index Mark 3 (HUI3) system is a generic HRQL instrument which was developed not only for measuring health status but also for economic evaluation. HUI3 includes a health-status classification system and a preference-based scoring formula. The HUI3 has eight attributes (vision, hearing, speech, ambulation, dexterity, emotion, cognition, and pain) with five to six levels per attribute. The multiplicative multi-attribute utility function for the HUI3 system can be used to generate utility scores for use in economic analysis.

i. Cost

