Heart Attack

Stroke

Diabetes

Other

Don't know

Did your natural father ever have any of the following?

Diabetes Yes No I don't know

High blood pressure Yes No I don't know

Stroke Yes No I don't know

Heart Attack Yes No I don't know

I don't know if my natural father is living.

3. How many full brothers and sisters do you have? Include any brothers or sisters who may have died, but do not include any half or step brothers or sisters. Check the "don't know" box if you don't know.

Number of brothers

I don't know

Number of sisters

I don't know

4. How many of them have had:

(Check the "don't know" box if you don't know how many have had these conditions.)

	Number of brothers	Number of sisters
Diabetes	  Number  Don't know	  Number  Don't know
High blood pressure	  Number  Don't know	  Number  Don't know
Heart attack	  Number  Don't know	  Number  Don't know
Stroke	  Number  Don't know	  Number  Don't know

HEALTH UTILITIES INDEX III (HUI-3)

This questionnaire contains a set of questions which ask about various aspects of your health. When answering these questions please think about your health and your ability to do things on a day-to-day basis, during the past 4 weeks. To define the 4 week period, please think about what the date was 4 weeks ago and recall the major events that you have experienced during this period. Please focus your answers on your abilities, disabilities and how you have felt during the past 4 weeks.

You may feel that some of these questions do not apply to you, but it is important that we ask the same questions of everyone. Also, a few questions are similar; please excuse the apparent overlap and answer each question independently.

Please read each question and consider your answers carefully. For each question, please select one answer that best describes your level of ability or disability during the past 4 weeks. Please indicate the selected answer by circling the letter (a, b, c, ...) beside the answer.

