- c. Somewhat unhappy.
- d. Very unhappy.
- e. So unhappy that life was not worthwhile.

8. Which one of the following best describes the pain and discomfort you have experienced during the past 4 weeks?

- a. Free of pain and discomfort.
- b. Mild to moderate pain or discomfort that prevented no activities.
- c. Moderate pain or discomfort that prevented some activities.
- d. Moderate to severe pain or discomfort that prevented some activities.
- e. Severe pain or discomfort that prevented most activities.

9. Which one of the following best describes your ability, during the past 4 weeks, to walk?

Note: Walking equipment refers to mechanical supports such as braces, a cane, crutches or a walker.

- a. Able to walk around the neighborhood without difficulty, and without walking equipment.
- b. Able to walk around the neighborhood with difficulty; but did not require walking equipment or the help of another person.
- c. Able to walk around the neighborhood with walking equipment, but without the help of another person.
- d. Able to walk only short distances with walking equipment, and required a wheelchair to get around the neighborhood.
- e. Unable to walk alone, even with walking equipment. Able to walk short distances with the help of another person, and required a wheelchair to get around the neighborhood.
- f. Unable to walk at all.

10. Which one of the following best describes your ability, during the past 4 weeks, to use your hands and fingers?

Note: Special tools refers to hooks for buttoning clothes, gripping devices for opening jars or lifting small items, and other devices to compensate for limitations of hands or fingers.

- a. Full use of two hands and ten fingers.
- b. Limitations in the use of hands or fingers, but did not require special tools or the help of another person.
- c. Limitations in the use of hands or fingers, independent with use of special tools (did not require the help of another person).
- d. Limitations in the use of hands or fingers, required the help of another person for some tasks (not independent even with use of special tools).
- e. Limitations in the use of hands or fingers, required the help of another person for most tasks (not independent even with use of special tools).
- f. Limitations in the use of hands or fingers, required the help of another person for all tasks (not independent even with use of special tools).

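### Two adjacent answers of HUI-3 item 8 (pain) state the same activity limit with overlapping intensity, so the recorded pain level can move without a change in health

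*Combined protocol and SAP*

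**What the plan says.** The HUI-3 form in Appendix B asks in item 8: "Which one of the following best describes the pain and discomfort you have experienced during the past 4 weeks". Its general instruction is to give a single best answer: "please select one answer that best describes your level of ability or disability during the past 4 weeks". After a pain-free option a, the grades start at b, where pain is mild to moderate and nothing is given up because of it, and end at e, where pain is severe and most of what the respondent does is affected. Of the two grades in between, option d is worded "Moderate to severe pain or discomfort that prevented some activities", while the grade just below it, option c, is worded "Moderate pain or discomfort that prevented some activities".

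Section III.H.h (Health-Related Quality of Life) lists pain among the eight HUI3 attributes, each with five to six levels, and describes a preference-based scoring formula. On its use, the section says: "The multiplicative multi-attribute utility function for the HUI3 system can be used to generate utility scores for use in economic analysis". Table 3 in section III.H schedules the Health Utilities Index at baseline, F06, F12 and F24. Section II (Specific Aims) puts health-related quality of life in the fourth aim.

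**The concern.** A scored item needs answers that separate health states, so that one state leads to one level. In item 8 the third and fourth answers share an activity limit, and the intensity of one contains that of the other. One person with the same pain at two visits, or two people with the same pain, could mark different answers. A multi-attribute utility would then register a difference that is not there. Pain is relevant in this trial: the lifestyle arm builds up to 180 minutes of exercise a week (section III.F.a), and injuries and orthopedic conditions are monitored as possible adverse effects (section IX). At stake are the HUI3 utility, the quality-of-life comparison, and any economic analysis that uses the utility.

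**Working it through.** No figure in the plan depends on this item, so there is nothing to reproduce. The check is a reading of the form, followed by an illustration on assumed values.

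**Adjacent options compared**

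| Option | Intensity | Activity limit |
|---|---|---|
| b | mild to moderate | none |
| c | moderate | some |
| d | moderate to severe | some |
| e | severe | most |

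- a/b: separated by absence or presence of pain.
- b/c: separated by activity limit (none, some).
- c/d: same activity limit, and moderate is part of moderate to severe. Not cleanly separated.
- d/e: separated by activity limit (some, most).

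The intensity bands of neighbours touch all the way from b to e, so the activity limit has to do the separating. It fails for one of the four adjacent pairs. By contrast, item 10 on the same form steps its last three options through some, most and all tasks. That suggests a slip in item 8 rather than intent.

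**Link to the score.** Item 8 has five options, and section III.H.h gives five to six levels per attribute. That item 8 sets the pain level, with c and d as separate levels, is inferred from this. The documents do not print the scoring map, and item 15 is a second pain question, graded by frequency and relief.

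**Illustration.** None of the following inputs is in the documents. Assume a utility gap g of 0.05 to 0.15 between c and d, a share p of 10% to 30% of participants in the overlapping state at both visits, and an independent even choice between c and d at each visit.

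- Shift in mean utility at one visit, against everyone in that state marking c: p × g / 2 = 0.10 × 0.05 / 2 = 0.0025, up to 0.30 × 0.15 / 2 = 0.0225. If it is alike in both arms, it cancels from their difference.
- For a participant in that state, the spurious change is +g or −g with probability 1/4 each, otherwise 0. SD = g × √0.5 = 0.035 to 0.106.
- Over the whole sample: SD = g × √(0.5p) = 0.05 × √0.05 = 0.011, up to 0.15 × √0.15 = 0.058.
- With 225 randomized 2:1 (section III.E.b), that is 150 and 75 with no dropout, √(1/150 + 1/75) = 0.141. The contribution to the standard error of the arm difference in change is 0.011 × 0.141 = 0.0016, up to 0.058 × 0.141 = 0.0082. It adds in quadrature to ordinary sampling error.

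The even choice is close to a worst case, for the reason given under the objection.

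**The case against.** The strongest reply is that the options do differ in intensity and the respondent is asked for the best description. For purely moderate pain that stopped some activities, c is the exact match and d the looser one. This stands in part: it makes c the more likely choice and an even split pessimistic. It does not remove the overlap, because d also covers moderate pain with the same limit, and nothing tells respondents or staff how to choose. The form's notice that "a few questions are similar; please excuse the apparent overlap and answer each question independently" does not help either, since it concerns similar questions and not answers within one question. Blurred neighbouring grades also occur in item 12 (a little versus some difficulty), but there the wording is at least different.

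The reach is also narrow, and this stands in full. Section II frames cost-effectiveness in terms of the primary and major secondary outcomes, not utilities. Section III.H.h says only that the utility function can be used for economic analysis. Section IV (Analytical Plan) names no HUI3 analysis. Section III.H also puts questionnaires under Steering Committee approval, so a review step exists, and the documents do not show that this English print is the form participants received.

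A reader might go further and infer three things that the documents do not support:

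- **That the arm comparison is biased.** This would need the c/d choice to differ by arm for the same pain. Participants are unmasked and only one arm gets the exercise program, so it is conceivable, but nothing in the documents shows or quantifies it.
- **That the utilities are no longer comparable with HUI3 values from other studies.** This follows only if the printed line departs from the licensed text, which is not in the documents.
- **That the spurious-change SD of 0.035 to 0.106 describes the trial.** It applies only to participants in the overlapping state. Over the whole sample, the same assumptions give 0.011 to 0.058.

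**Conclusion.** The overlap is real and visible in the form's own words: options c and d of item 8 do not describe distinct states. The pain level can therefore change between visits without a change in health, though it need not. The expected consequence is added noise in the HUI3 utility and the quality-of-life comparison under the fourth aim. Its size cannot be derived from the documents; on the assumed inputs above it is small. The conclusion assumes that item 8 feeds the HUI3 pain attribute with c and d as separate levels, and that the printed form is the one administered. The HbA1c outcome, its analysis and the sample size do not depend on this item. Severity: minor.

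**What to change.** Before the form is used, compare options c and d of item 8 with the licensed HUI questionnaire in every language version administered. If the printed line departs from that text, correct it so that each option states a distinct degree of activity limitation. If it agrees, leave it and note that it was checked. In either case, record which version was used at which visits.

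If forms have already been completed with the printed wording, flag them and report one sensitivity analysis of HUI3 utility with c and d merged: score all c and d answers at the weight for c, then all at the weight for d, and show whether the arm comparison changes.

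The cost is a version check and at most a one-line correction per language, plus a short analysis if data already exist. No extra visits or staff are needed.
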